7.3. ACCOUNTABILITY ON SITE AND RETURN/DESTRUCTION OF INVESTIGATIONAL PRODUCT(S)

The Investigator should maintain accurate written records of drugs received, dispensed, returned and any remaining treatment units, on the drug accountability form. The packaging of the medication should remain intact until just before the dispensation.

At the end of the study, all used and unused treatments including packaging should be noted, and local destruction or return is organised by the appointed CRA. A copy of the drug accountability form should be provided by the Investigator to the CRA.

8. CONCOMITANT TREATMENTS

Any existing concomitant treatment, any new concomitant treatment or change in the dosage of an existing concomitant treatment during the course of the study must be noted on the CRF.

For all concomitant treatments taken during the study, the following information must be noted in the relevant section(s) of the CRF:

- The name of the treatment and its form
- The reason for prescription
- The route of administration
- The daily dose
- The duration.

9. EVALUATION CRITERIA

9.1. EFFICACY ASSESSMENT

9.1.1. Primary endpoint

Primary outcome will be the detection of the percentage of patients after 4 weeks of edoxaban treatment with complete thrombus resolution by TEE, evaluated with the following Probe angulations: 0°, 45°-to-60°, 90°.

9.1.2. Secondary endpoint

Secondary endpoints will be:

- Absolute and percent variation of thrombus area at 4 weeks by TEE evaluation (Probe angulations: 0°, 45-to-60°, 90°)
- Time to electrical cardioversion (when applicable).

9.2. SAFETY ASSESSMENT

- Incidence of bleeding events at 4 weeks and after 8 weeks (telephone assessment) after the end of treatment
- Incidence of any stroke or peripheral embolism at 4 weeks and after 8 weeks (telephone assessment) after the end of the treatment.

9.2.1. Definition of major bleeding

Major bleeding will be defined as follows (11) and reported as SAEs or AEs as described in Section 11:

1. Fatal bleeding, and/or
2. Symptomatic bleeding in a critical area or organ, such as intracranial, intraspinal, intraocular, retroperitoneal, intraarticular or pericardial, or intramuscular with compartment syndrome, and/or
3. Bleeding causing a fall in hemoglobin level of 20 g/L (1.24 mmol/L) or more, or leading to transfusion of two or more units of whole blood or red cells.

9.2.2. Non-major bleeding

Clinically relevant non-major bleeding (12) will be defined as bleeding that did not fall under the category of major bleeding, but corresponded to any of the following:

1. hematoma of 5 cm in longest diameter
2. epistaxis or gingival bleeding that occurred in the absence of external factors and lasts ≥ 5 minutes
3. GI bleeding
4. gross hematuria that is persistent after 24 hours of onset, and
5. other bleeding that was assessed to be clinically significant by the investigator or sub-investigator.

Any bleeding event that did not meet major or clinically relevant non-major bleeding criteria will be categorized as a minor bleeding event.

9.2.3. Stroke and thrombotic events

Thrombotic events will be defined as and reported as SAEs or AEs, as described in section 11.

1. Ischemic stroke
2. Transient ischemic attack (TIA)
3. Deep vein thrombosis (with or without pulmonary embolism)
4. Any other form of systemic embolism.

9.2.4. Adverse Events

At Inclusion, any concomitant disease will be reported on the CRF. At each further visit, the occurrence of adverse events (AEs) since the last visit will be based on the patient's or patient parents' spontaneous oral reporting, the investigator's non-leading questioning and his/her clinical evaluation. Any AE reported will be re-assessed by the investigator through complementary questioning, and noted in the medical file. All AEs will be reported on the CRF.

9.3. COMPLIANCE

The patient will be reminded to bring back, at each visits, any remaining tablets, boxes (used or unused). At the follow-up visit, the Investigator will record the number of supplied and remaining tablet in the CRF.

Considering the duration of the study, compliance will be judged as:

- Complete if $\geq 100\%$ taken (28 tablets or more)
- Adequate if $\geq 75\%$ and $< 100\%$ taken (at least 21 tablets)
- Non adequate if $< 75\%$ taken (less than 21 tablets).

10. STUDY PROCEDURES

Each patient considered eligible for selection by the Investigator will be informed of the characteristics and the consequences of the trial both verbally and by reviewing the patient's information sheet and consent form approved by the competent EC. Acceptance to participate

in the study will be subordinated to the signature of the informed consent. A copy will be keep by the patient.

10.1. BASELINE VISIT

A screening assessment can occur on the same day of the baseline visit or up to 7 days before it. The patient will be assessed for the following:

- Collection of the signed informed consent
- Verification of inclusion/exclusion criteria
- Collection of demographic data, including: date of birth (month and year), gender, weight, height (calculated BMI), and race
- Medical history (with evaluation of CHA₂DS₂-VAS_C score and HAS-BLED scores)
- Information regarding AF
- Blood pressure, heart rate
- ECG
- Transthoracic echocardiogram (TTE)
- Transesophageal echocardiogram (TEE)
- Therapy: antithrombotic treatment and concomitant treatments (antihypertensives, heart failure and antiarrhythmic therapies, metabolic and anti-inflammatory, antithrombotic therapies for indications other than AF), and other selected drugs.
- Complete blood count; assessment of liver and renal function.

10.2. FOLLOW-UP (WEEK 4)

After four weeks of treatment, the patient will be visited and assessed for the following:

- Serious adverse events, including hospitalizations, life threatening events and death
- Non-serious adverse events
- Information regarding AF
- Concomitant diseases (current, any change)
- Adherence to the study treatment

- Therapy (current, any change)
- Blood pressure, heart rate
- ECG
- Transthoracic echocardiogram (TTE)
- Transesophageal echocardiogram (TEE)
- Complete blood count; assessment of liver and renal function.

10.3. FINAL TELEPHONE ASSESSMENT (WEEK 8)

- Serious adverse events, including hospitalizations, life threatening events and death
- Non-serious adverse events
- The investigator will also complete the final study form.

10.4. ASSESSMENTS AND PROCEDURES

10.4.1. Stroke risk index

The CHA₂DS₂-VAS_c (Cardiac failure, Hypertension, Age doubled, Diabetes, Stroke doubled, Vascular, Age, Sex) composite stroke risk index is based on a point system in which 2 points are assigned for age ≥ 75 years and for a history of stroke or TIA and 1 point each is assigned for a history of hypertension, diabetes, recent cardiac failure, vascular diseases, age <75 years, and female gender (13).

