Diagnosis and Criteria for Inclusion:	
Inclusion criteria
 
Patients with all the following criteria will be eligible for inclusion in the study protocol:
 
 1. Signed written informed consent. 2. Males and females ≥ 18 years of age. 3. Female subjects must be post-menopausal (for at least 2 years), surgically sterile, abstinent, or, if sexually active, be practicing an effective method of birth control (e.g., prescription oral contraceptives, contraceptive injections, intrauterine device, double-barrier method, contraceptive patch, male partner sterilization) before entry and throughout the study; and, for those of 	

	
childbearing potential, have a negative serum β-hCG pregnancy test at screening.
 
4. Atrial fibrillation (AF) must be documented by ECG evidence (e.g., 12-lead ECG, rhythm strip, Holter, pacemaker interrogation) within 30 days before enrolment.
 
5. Subjects with newly diagnosed atrial fibrillation are eligible provided that:
 
• -there is evidence that the atrial fibrillation is non-valvular;• -there is ECG evidence on 2 occasions 24 hours apart demonstrating atrial fibrillation. 
6. LA or LAA thrombosis documented by trans-esophageal echocardiography (TEE)
 
7. CHA₂DS₂-VAS_C score >1.

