Statistical Methods:	
Sample Size There are no previous studies conducted with edoxaban on atrial thrombus dissolution and this is a pilot trial. For this reason sample size has been determined empirically, on the basis of case reports with similar products in this clinical conditions (6, 8-10, 15). However, if the proportion of patients with thrombus dissolution after 4 weeks of treatment will be 60%, which is compatible with the above mentioned case reports, a sample size of 25 produces a two-sided 95% confidence interval with range 39-79%.
 
Primary Analysis Primary outcome will be the detection of the percentage of patients, after 4 weeks of edoxaban treatment, with complete thrombus resolution by TEE, evaluated with the following Probe angulations: 0°, 45°-to-60°, 90°. As this is a single arm, open-label study, in principle, only a descriptive statistical analysis will be performed for the primary criterion.
 
Secondary analyses Secondary endpoints will be: absolute and percent variation of thrombus area at 4 weeks by TEE evaluation (Probe angulations: 0°, 45-to-60°, 90°) and time to electrical cardio-version (when applicable). Only a descriptive statistical analysis will be performed for the secondary criterion.
 
Safety analysis Analyses of the safety criteria that will include: percentage of bleeding events at 4 weeks and after 8 weeks (telephone assessment) after the end of the treatment; percentage of any stroke or peripheral embolism at 4 weeks and after 8 weeks (telephone assessment) after the end of the treatment; percentage of any other safety related events (deaths, SAEs and AEs).

Study flow-chart

Timing	BASELINE	FOLLOW-UP	PHONE ASSESSMENT
	Day 0	Week 4 (± 3 days)	Week 8 (± 3 days)
Confirmation of consent	■		
Verification of inclusion/exclusion criteria	■		
Demographic data	■		
Medical history	■		
CHA ₂ DS ₂ -VAS _C score and HAS-BLED score	■		
Information regarding AF	■	■	
Blood pressure, heart rate	■	■	
EKG	■	■	
Transthoracic echocardiogram	■	■	
Transesophageal echocardiogram	■	■	
Blood count; liver and renal function	■	■	
Concomitant treatments	■	■	
Bleeding events		■	■
Thromboembolic events		■	■
Other adverse events		■	■
Study drug dispensation	■		
Compliance		■	
Study completion form			■

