1.2. LIST OF ABBREVIATIONS

ADR	: Adverse Drug Reaction
AE	: Adverse Event
AF	: Atrial Fibrillation
ALT	: Alanine aminotransferase
AST	: Aspartate aminotransferase
ATC	: Anatomical Therapeutic Chemical Classification System
CHA ₂ DS ₂	: Cardiac failure, Hypertension, Age (x2), Diabetes, Stroke (x 2) risk index
CI	: Confidence Interval
CRA	: Clinical Research Associate
CRF	: Case Report Form
DBP	: Diastolic Blood Pressure
EC	: Ethic Committee
ECG	: Electrocardiogram
FAS	: Full Analysis Set
GCP	: Good Clinical Practice
HR	: Hazard Ratio
ICH	: International Conference on Harmonisation
LA	: Left Atrial
LAA	: Left Atrial Appendage
MedDRA	: Medical Dictionary for Regulatory Activities
NOAC	: Non vitamin K oral anticoagulants
OAC	: Oral Anticoagulant Therapy
PP	: Per Protocol
SAE	: Serious Adverse Event
SBP	: Systolic Blood Pressure
SEE	: Systemic Embolic Events
SmPC	: Summary of Product Characteristics
TEE	: Trans Esophageal Echocardiography
ULN	: Upper Level of Normal
VKA	: vitamin K antagonists
WHO	: World Health Organization

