6.1. INCLUSION CRITERIA

Patients with all the following criteria will be eligible for inclusion in the study protocol:

1. Signed written informed consent
2. Males and females \geq 18 years of age
3. Female subjects must be postmenopausal (for at least 2 years), surgically sterile, abstinent, or, if sexually active, be practicing an effective method of birth control (e.g., prescription oral contraceptives, contraceptive injections, intrauterine device, double-barrier method, contraceptive patch, male partner sterilization) before entry and throughout the study; and, for those of childbearing potential, have a negative serum β -hCG pregnancy test at screening
4. Atrial fibrillation (AF) must be documented by ECG evidence (e.g., 12-lead ECG, rhythm strip, Holter, pacemaker interrogation) within 30 days before enrolment.
5. Subjects with newly diagnosed atrial fibrillation are eligible provided that:
 - a. there is evidence that the atrial fibrillation is non-valvular
 - b. there is ECG evidence on 2 occasions 24 hours apart, demonstrating atrial fibrillation
6. LA or LAA thrombosis documented by transesophageal echocardiography (TEE)

7. CHA₂DS₂-VASc score >1.

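### Section 10.4.1 gives one CHA₂DS₂-VASc point for any age under 75 with no lower limit, so scoring from it loosens inclusion criterion 7

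*Protocol*

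**What the plan says.** Section 10.4.1 is the only place where the protocol says how the index is scored. For age it has two items. The first is "2 points are assigned for age ≥ 75 years". The second is in the list of one-point items: "1 point each is assigned for a history of hypertension, diabetes, recent cardiac failure, vascular diseases, age <75 years, and female gender". In the same sentence, the expansion of the acronym names age twice, as two separate components: "Age doubled, Diabetes, Stroke doubled, Vascular, Age, Sex".

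The score is used in two ways. Inclusion criterion 7 in section 6.1 requires "CHA₂DS₂-VASc score >1", and the synopsis says the same. The score is also recorded at baseline (section 10.1 and the study flow-chart). Inclusion criterion 2 sets the lowest age: "Males and females ≥ 18 years of age".

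No other section supplies a lower limit for the one-point age item. The abbreviation list expands only the shorter index: "Cardiac failure, Hypertension, Age (x2), Diabetes, Stroke (x 2) risk index". The age item in section 10.4.2 belongs to HAS-BLED, a different score.

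**The concern.** From age 18 upward, the two age items together cover everyone: a patient is either under 75 (one point) or 75 and over (two points). The one-point item therefore separates nobody under 75, although the sentence lists it as a risk component in its own right. An item that every younger adult meets adds a constant and carries no information about risk. The natural reading is that a lower age limit was lost in drafting.

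The extra point matters because it feeds an entry criterion. As written, an 18-year-old woman with no risk factor scores 2 (one for age, one for sex) and meets criterion 7. That sits badly with sections 2.2, 5.2.1 and 6, which describe the population as at high thromboembolic or stroke risk. It also sits badly with section 2.5, which uses the same threshold in its case that anticoagulation is needed in any event. With 6–8 sites, one site scoring from the protocol and another from the cited source could give the same patient different scores.

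**Working it through.** The protocol states no figure for this score, so there is none to reproduce. The check lists every possible profile and counts how many pass criterion 7 under each reading.

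**Inputs**

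| Item | Points | Source |
|---|---|---|
| Prior stroke or TIA | 2 | 10.4.1 |
| Hypertension, diabetes, cardiac failure, vascular disease | 1 each | 10.4.1 |
| Female sex | 1 | 10.4.1 |
| Age 75 and over | 2 | 10.4.1 |
| Age under 75, as written | 1 | 10.4.1 |
| Pass mark | score above 1 | 6.1, criterion 7 |
| Lowest age | 18 | 6.1, criterion 2 |

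*Assumption:* the one-point age item was meant to carry a lower limit somewhere between 18 and 75. Its value is not needed, because the counts are the same wherever it lies.

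**Step 1: profiles.** Two sexes and five yes/no factors give 2 × 2⁵ = 64 profiles in each age band. Let N be the non-age score:

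N = 2 × stroke/TIA + hypertension + diabetes + cardiac failure + vascular disease + female

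N runs from 0 to 2 + 5 = 7.

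- N = 0: 1 profile (man, no factor).
- N = 1: 5 profiles (man with only hypertension, only diabetes, only cardiac failure or only vascular disease; woman with no factor).
- N ≥ 2: 64 − 6 = 58 profiles.

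**Step 2: below the missing limit.**

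| | Score | Range | Fail (score ≤ 1) | Pass |
|---|---|---|---|---|
| With a lower limit | N | 0–7 | N ≤ 1: 6 of 64 | 58 |
| As written | N + 1 | 1–8 | N = 0: 1 of 64 | 63 |

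Newly passing: 63 − 58 = 5, and 5/64 = 7.8%. Among male profiles, failures drop from 5 of 32 to 1 of 32; among female profiles, from 1 of 32 to 0 of 32. All 64 scores are one point higher as written.

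A man whose only factor is prior stroke or TIA scores 2 with a limit and 3 as written, so he passes either way.

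**Step 3: the other age bands.** From the limit to 74, the age item gives one point under both readings and 1 of 64 profiles fails. At 75 and over it gives two points, the range is 2–9 and none fails. Over all three bands (3 × 64 = 192 profiles):

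- as written: 1 + 1 + 0 = 2 fail;
- with a limit: 6 + 1 + 0 = 7 fail;
- difference: 5/192 = 2.6%, all of it below the limit.

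**The case against.** The strongest reply is that criterion 7 names an established index and does not point to section 10.4.1. That section is a one-sentence description that closes by citing its source (reference 13), and section 2.5 ties the same threshold to the cited guideline. A site that scores from the source makes no error, and nothing in the protocol says that sites will score from 10.4.1. This stands as a limit on the effect, which is conditional. It does not remove the error: the protocol's only scoring rule gives the wrong answer when followed.

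A second reply is that the two age items are complementary and so do not contradict each other, and that the document does not show what the right rule is. It is true that the limit cannot be read from the protocol, and none is supplied here. That a limit is missing rests on the text itself: age is listed as a component of its own, yet it distinguishes no one under 75.

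A third reply is that profile counts give a false sense of precision. In part this stands. The profiles are unweighted combinations, and 5 of 64 is not a share of patients. The count shows exactly which patients are affected, not how many of them will be enrolled.

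**Conclusion.** The point holds and is minor. Section 10.4.1 is wrong as written. The eligibility effect is confined to five profiles below the missing limit, and none changes at older ages. The baseline score is one point too high for every patient below the limit.

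Both effects assume that sites score from this text and not from reference 13. The protocol gives neither the limit nor the expected age mix, so the number affected among the 25 patients cannot be worked out and may be none.

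The consequence for the results is small. Every patient must still have left atrial or appendage thrombus documented by transesophageal echocardiography (criterion 6). No planned efficacy analysis uses the score. The primary estimate and the 39–79% interval in section 14.2 are unaffected.

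**What to change.** In section 10.4.1, state the lower age limit of the one-point age item, taken from the cited index (reference 13), so that criterion 7 and the recorded baseline score rest on one definition. This costs one line of text and changes nothing in the design, sample size or analysis.

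A separate wording correction, which adds no weight to this point, could go into the same amendment. The lead-in to the exclusion criteria, in section 6.2 and the synopsis, says that patients are excluded when they meet all of the listed criteria; it should say any. That is one word in each place.

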10.4.2. Bleeding risk index

HAS-BLED is a scoring system developed to assess the 1-year risk of major bleeding in patients with atrial fibrillation. A calculated HAS-BLED score is between 0 and 9, and based on one point assigned to each of the following parameters (14):

1. Hypertension: uncontrolled or >160 mmHg systolic)
2. Abnormal renal function: Dialysis, transplant, Cr >2.6 mg/dL or >200 μ mol/L
3. Abnormal liver function: Cirrhosis or Bilirubin >2 x ULN or AST/ALT/AP >3 x ULN
4. Stroke: Prior history of stroke
5. Bleeding: Prior Major Bleeding or Predisposition to Bleeding

6. Labile INR: (Unstable/high INRs), Time in Therapeutic Range < 60%
7. Elderly: Age > 65 years
8. Prior Alcohol or Drug Usage History
9. Medication Usage Predisposing to Bleeding: (Antiplatelet agents, NSAIDs).

11. ADVERSE EVENTS: DEFINITION AND REPORTING

11.1. ADVERSE EVENTS

11.1.1. Definition of Adverse Events

An adverse event is any adverse change from the patient's baseline condition, *i.e.* any subjective signs and symptoms, or change in a concomitant disease present at the Inclusion Visit considered related or not related to the treatment.

This includes intercurrent signs, symptoms and illnesses that may occur during the course of the clinical study.

11.1.2. Grading of Adverse Events

Adverse or intercurrent events are graded as follows:

- Mild: awareness of signs or symptoms, but easily tolerated
- Moderate: uncomfortable enough to cause interference with usual activity
- Severe: incapacity with inability to work or do usual activity

11.1.3. Reporting of Adverse Events

The records of adverse events in the CRF describe the nature (diagnosis, signs and symptoms), severity, onset date, stop date, outcome and actions taken, and the relationship to study

treatment (in the Investigator's opinion). It must be specified whether the event is serious or not.

11.2. SERIOUS ADVERSE EVENTS (SAE)

11.2.1. Definition

A serious adverse event (SAE) includes, but is not necessarily restricted to any event which:

- results in death (whatever may be the cause)
- is life-threatening
- results in persistent or significant disability/incapacity
- requires the patient's hospitalisation or prolongation of current hospitalisation. The following ill not be reported as a SAE: a) planned medical/surgical procedures decided or scheduled prior patient's signature of the informed consent; b) preparation for a routine health assessment/procedure; c) administrative or social reasons (e.g., lack of housing, economic inadequacy, care-giver respite, family circumstances)
- Is a congenital anomaly or birth defect.

Other events such as cancer, and any additional adverse experience occurring during the study period, defined by the protocol as serious, or which the Investigator considers significant enough, or that suggest a significant hazard, contra-indications, side effect or precaution, must be handled as serious adverse events.

Any overdosage meeting a seriousness criteria should be reported as a SAE.

11.2.2. Reporting of SAE

All serious adverse events, according to the above-mentioned definitions and regardless of treatment or relationship to study drug, must be recorded by the Investigator as soon as he/she is informed of the event.

The Investigator must notify the Promoter about this event by sending, within 24 hours, the "Notification of serious adverse event" form ("first notification") reported in Appendix 17.2 of

the study protocol, with all the available information about the event to the Promoter's pharmacovigilance unit:

Contact	Number or address	Instruction or comment
e-mail	[contact] (24 hours coverage)	Please attach PDF scan of the SAE form
[contact] hours coverage)	If not possible to send the report by e-mail
[contact] (business hours)	Only if it is not possible to send a paper report

11.2.3. Follow-up of SAE

The Investigator must design a specific clinical report and use the "Notification of serious adverse event" form ("follow-up"), and collect the results of the carried-out examinations and the reports of hospitalization.

Serious adverse events must be followed-up until resolution or stabilisation.

11.2.4. SAE Occurring After the Study

Because of the 4 week follow-up after the end of treatment, any SAE occurring after the end of the study last follow-up visit will not be notified to the Promoter.

However, the Promoter must be notified of any event occurring at any time after the end of the study (last follow-up visit) for the patient who may be related to the study treatment in the Investigator's opinion.

